18. PHARMACOKINETIC ANALYSIS

18.1. POPULATION PHARMACOKINETIC ANALYSIS

All plasma concentrations of SEP-363856 and SEP-363854 will be presented in data listings.

Document: Documentation\SAP

Author:

Version Number:

Final V1.0

Version Date:

27FEB2019

Template No: CS_TP_BS016 Revision 4
 Effective Date: 01Apr2016

Reference: CS_WI_BS005

Copyright © 2009, 2010, 2012, 2016 Quintiles Transnational Corp. All rights reserved.

The contents of this document are confidential and proprietary to Quintiles Transnational Corp. Unauthorized use, disclosure or reproduction is strictly prohibited.

Population pharmacokinetic (PK) analysis will be performed using plasma SEP-363856 concentrations. The analysis will be reported separately.

18.2. PHARMACODYNAMIC ANALYSIS

The relationship between PANSS total score and plasma SEP-363856 exposure using population PK/pharmacodynamics (PD) methods will be explored. The results will be reported separately.

The impact of cytochrome (CYP) P450 CYP2D6 metabolizer status on plasma SEP-363856 exposure will be explored. The results will be reported separately.

19. DATA NOT SUMMARIZED OR PRESENTED

Not applicable.

20. CHANGES IN THE ANALYSIS SPECIFIED IN THE STATISTICAL ANALYSIS PLAN

Any changes or deviations during the analysis and reporting process from the statistical analysis plan designed will be described and justified in the final report.

APPENDIX 1. PROGRAMMING CONVENTIONS FOR OUTPUTS

OUTPUT CONVENTIONS

Where applicable, the Appendix_Compilation_Working_Guidelines_Final 07May2014 .pdf document – provided by Sunovion – will be followed.

In addition, the following output conventions are to be followed:

- o The first row in the body of the table or listing should be blank
- o The left hand column should start in column 1. No indenting or centering of the output should occur.
- o Rounding should be done with the SAS function ROUND.
- o Numbers in tables should be rounded, not truncated.
- o Alphanumeric output should be left aligned.
- o Numbers should be decimal point aligned.
- o Whole numbers should be right aligned.
- o Text values should be left aligned.
- o The first letter of a text entry should be capitalized.
- o The width of the entire output should match the linesize (134)
- Univariate Statistics:
 - o If the raw data has N decimal places, then the summary statistics should have the following decimal places:
 - o Minimum and maximum: N
 - o Mean, median, Q1, and Q3: N + 1
 - o SD: N + 2
 - Frequencies and percentages (n and %):
 - o Percent values should be reported inside parentheses, with one space between the count (n) and the left parenthesis of the percentage. Parentheses should be justified to accept a maximum of 100.0 as a value and padded with blank space if the percent is less than 100.0.
 - o Percentages will be reported to one decimal place, except cases where percent <100.0% but >99.9% will be presented as '>99.9%' (e.g., 99.99% is presented as >99.9%); and cases where percent < 0.1% will be presented as '<0.1%' (e.g., 0.08% is presented as <0.1%). Rounding will be applied after the <0.1% and >99.9% rule.
 - o Where counts are zero, no percentage should appear in the output.
 - Confidence Intervals:
 - o Confidence intervals and estimates are presented to one place more than the raw data, and standard errors to two places more than the raw data.
 - o Confidence intervals should be justified so that parentheses displayed on consecutive lines of a table “line up”.
 - o Boundary values of confidence intervals should be separated by a comma.

Document: Documentation\SAP

Author:

Version Number:
 Version Date:

Final V1.0
 27FEB2019

Template No: CS_TP_BS016 Revision 4
 Effective Date: 01Apr2016

Reference: CS_WI_BS005

Statistical Analysis Plan

- o Boundary values should be padded as necessary to accept negative values and to allow alignment of the decimal place.
- Ratios:
 - o Ratios should be reported to one more decimal place than the raw data.
- Spacing:
 - o There must be a minimum of 1 blank space between columns (preferably 2).
- Missing values:
 - o A “0” should be used to indicate a zero frequency.
 - o A blank will be used to indicate missing data in an end-of-text table or subject listing.
- Figures:
 - o Figures should be provided in RTF files using the SAS Output Delivery System (ODS), as Computer Graphics Metafile (CGM) formatted graphical output generated by SAS.
 - o The CGM file itself should contain the title or footer.
 - o The image should be clear and of high quality when viewed in the Word document, and when printed.
 - o In general, boxes around the figures should be used.
- Footers should be defined as follows:
 - o A continuous line of underscores (‘_’) will follow the body of the table or listing prior to any footnotes at the bottom of the page.
 - o Table footnotes should be defined using compute statements in the proc report, and should appear directly after the body of the table.
 - o If text wraps across more than one line (for a note), the first letter for all lines of text after the first one will be indented to align beneath the first letter of the text in the first line.

DATES & TIMES

Depending on data available, dates and times will take the form yyyy-mm-ddThh:mm:ss.

SPELLING FORMAT

English US.

PRESENTATION OF TREATMENT GROUPS

For outputs, treatment groups will be represented as follows and in that order, unless specified otherwise in the shell:

Document: Documentation\SAP

Author:

Version Number:

Final V1.0

Version Date:

27FEB2019

Template No: CS_TP_BS016 Revision 4
 Effective Date: 01Apr2016

Reference: CS_WI_BS005

Copyright © 2009, 2010, 2012, 2016 Quintiles Transnational Corp. All rights reserved.

The contents of this document are confidential and proprietary to Quintiles Transnational Corp. Unauthorized use, disclosure or reproduction is strictly prohibited.

Group	For Tables, Graphs and Listings
Received Placebo in 361-201; Received SEP-363856 (25, 50 or 75 mg/day) in 361-202	PBO-SEP
Received SEP-363856 (50 or 75 mg/day) in 361-201; Received SEP-363856 (25, 50 or 75 mg/day) in 361-202	SEP-SEP
All subjects who entered 361-202	ALL EXT

LISTINGS

All listings will be ordered by the following (unless otherwise indicated in the template):

- Actual treatment received,
- Subject ID,
- Date/Time (where applicable) - listings of adverse events, concomitant medications, medical histories etc. should be sorted in chronological order, with earliest adverse event, medication or history coming first,

Document: Documentation\SAP

Author:

Version Number:
Version Date:

Final V1.0
27FEB2019

Template No: CS_TP_BS016 Revision 4
Effective Date: 01Apr2016

Reference: CS_WI_BS005

APPENDIX 2. PARTIAL DATE CONVENTIONS

Imputed dates will not be presented in the listings.

ALGORITHM FOR ADVERSE EVENTS:

The algorithm below applies to all AE and pre-treatment event records contained in the 361-202 database.

“Date & time”: use this criterion when both date and time information is available. “Date”: use this criterion when only the date information is available and time information isn’t available.

‡By comparing reported term, coded term, and the start date (and time if available).

*The distinction between 361-201 pre-treatment event and 361-201 AE should be performed as specified in the 361-201 SAP.

START DATE	STOP DATE	ACTION
Known	Known	If start date & time < 361-202 open-label extension study med start date & time, then 361-201 pre-treatment event or 361-201 AE* If start date < 361-202 open-label extension study med start date, then 361-201 pre-treatment event or 361-201 AE* If start date & time >= 361-202 open-label extension study med start date & time, then 361-202 AE If start date > 361-202 open-label extension study med start date, then 361-202 AE If start date = 361-202 open-label extension study med start date and the record exists in 361-201 database‡, then 361-201 pre-treatment event or 361-201 AE* If start date = 361-202 open-label extension study med start date and the record does not exist in 361-201 database‡, then 361-202 AE

Document: Documentation\SAP

Author:

Version Number:

Final V1.0

Version Date:

27FEB2019

Template No: CS_TP_BS016 Revision 4
 Effective Date: 01Apr2016

Reference: CS_WI_BS005

Copyright © 2009, 2010, 2012, 2016 Quintiles Transnational Corp. All rights reserved.

The contents of this document are confidential and proprietary to Quintiles Transnational Corp. Unauthorized use, disclosure or reproduction is strictly prohibited.

Statistical Analysis Plan

START DATE	STOP DATE	ACTION
Known	Partial	
If start date & time < 361-202 open-label extension study med start date & time, then 361-201 pre-treatment event or 361-201 AE*
 
If start date < 361-202 open-label extension study med start date, then 361-201 pre-treatment event or 361-201 AE*
 
If start date & time >= 361-202 open-label extension study med start date & time, then 361-202 AE
 
If start date > 361-202 open-label extension study med start date, then 361-202 AE
 
If start date = 361-202 open-label extension study med start date and the record exists in 361-201 database[‡], then 361-201 pre-treatment event or 361-201 AE*
 
If start date = 361-202 open-label extension study med start date and the record does not exist in 361-201 database[‡], then 361-202 AE

Known	Missing	
If start date & time < 361-202 open-label extension study med start date & time, then 361-201 pre-treatment event or 361-201 AE*
 
If start date < 361-202 open-label extension study med start date, then 361-201 pre-treatment event or 361-201 AE*
 
If start date & time >= 361-202 open-label extension study med start date & time, then 361-202 AE
 
If start date > 361-202 open-label extension study med start date, then 361-202 AE
 
If start date = 361-202 open-label extension study med start date and the record exists in 361-201 database[‡], then 361-201 pre-treatment event or 361-201 AE*
 
If start date = 361-202 open-label extension study med start date and the record does not exist in 361-201 database[‡], then 361-202 AE

Document: Documentation\SAP

Author:

Version Number:

Final V1.0

Version Date:

27FEB2019

Template No: CS_TP_BS016 Revision 4
 Effective Date: 01Apr2016

Reference: CS_WI_BS005

Copyright © 2009, 2010, 2012, 2016 Quintiles Transnational Corp. All rights reserved.

The contents of this document are confidential and proprietary to Quintiles Transnational Corp. Unauthorized use, disclosure or reproduction is strictly prohibited.

Statistical Analysis Plan

START DATE	STOP DATE	ACTION
Partial, but known components show that it cannot be on or after 361-202 study med start date	Known	361-201 pre-treatment event or 361-201 AE*
Partial, but known components show that it cannot be on or after 361-202 open-label extension study med start date	Partial	361-201 pre-treatment event or 361-201 AE*
Partial, but known components show that it cannot be on or after 361-202 open-label extension study med start date	Missing	361-201 pre-treatment event or 361-201 AE*
Partial, could be on or after 361-202 open-label extension study med start date	Known	
If stop date & time < 361-202 open-label extension study med start date & time, then 361-201 pre-treatment event or 361-201 AE*
 
If stop date < 361-202 open-label extension study med start date, then 361-201 pre-treatment event or 361-201 AE*
 
If stop date & time >= 361-202 open-label extension study med start date & time and the record exists in 361-201 database[‡], then 361-201 pre-treatment event or 361-201 AE*
 
If stop date & time >= 361-202 open-label extension study med start date & time and the record does not exist in 361-201 database[‡], then 361-202 AE
 
If stop date >= 361-202 open-label extension study med start date and the record exists in 361-201 database[‡], then 361-201 pre-treatment event or 361-201 AE*
 
If stop date >= 361-202 open-label extension study med start date and the record does not exist in 361-201 database[‡], then 361-202 AE

Document: Documentation\SAP

Author:

Version Number:

Final V1.0

Version Date:

27FEB2019

Template No: CS_TP_BS016 Revision 4
 Effective Date: 01Apr2016

Reference: CS_WI_BS005

Copyright © 2009, 2010, 2012, 2016 Quintiles Transnational Corp. All rights reserved.

The contents of this document are confidential and proprietary to Quintiles Transnational Corp. Unauthorized use, disclosure or reproduction is strictly prohibited.

Statistical Analysis Plan

START DATE	STOP DATE	ACTION
Partial, could be on or after 361-202 open-label extension study med start date	Partial	Impute stop date as latest possible date (i.e. last day of month if day unknown or 31st December if day and month are unknown). Then: If stop date & time < 361-202 open-label extension study med start date & time, then 361-201 pre-treatment event or 361-201 AE* If stop date < 361-202 open-label extension study med start date, then 361-201 pre-treatment event or 361-201 AE* If stop date & time >= 361-202 open-label extension study med start date & time and the record exists in 361-201 database [‡] , then 361-201 pre-treatment event or 361-201 AE* If stop date & time >= 361-202 open-label extension study med start date & time and the record does not exist in 361-201 database [‡] , then 361-202 AE If stop date >= 361-202 open-label extension study med start date and the record exists in 361-201 database [‡] , then 361-201 pre-treatment event or 361-201 AE* If stop date >= 361-202 open-label extension study med start date and the record does not exist in 361-201 database [‡] , then 361-202 AE.
Partial, could be on or after 361-202 open-label extension study med start date	Missing	If the record exists in 361-201 database [‡] , then 361-201 pre-treatment event or 361-201 AE* If the record does not exist in 361-201 database [‡] , then 361-202 AE

Document: Documentation\SAP

Author:

Version Number:

Final V1.0

Version Date:

27FEB2019

Template No: CS_TP_BS016 Revision 4
 Effective Date: 01Apr2016

Reference: CS_WI_BS005

Copyright © 2009, 2010, 2012, 2016 Quintiles Transnational Corp. All rights reserved.

The contents of this document are confidential and proprietary to Quintiles Transnational Corp. Unauthorized use, disclosure or reproduction is strictly prohibited.

START DATE	STOP DATE	ACTION
Partial, known components show that it is on or after 361-202 open-label extension study med start date	Known	If start date & time >= 361-202 open-label extension study med start date & time, then 361-202 AE If start date > 361-202 open-label extension study med start date, then 361-202 AE If start date = 361-202 open-label extension study med start date and the record exists in 361-201 database [‡] , then 361-201 pre-treatment event or 361-201 AE* If start date = 361-202 open-label extension study med start date and the record does not exist in 361-201 database [‡] , then 361-202 AE
Partial, known components show that it is on or after 361-202 open-label extension study med start date	Partial	If start date & time >= 361-202 open-label extension study med start date & time, then 361-202 AE If start date > 361-202 open-label extension study med start date, then 361-202 AE If start date = 361-202 open-label extension study med start date and the record exists in 361-201 database [‡] , then 361-201 pre-treatment event or 361-201 AE* If start date = 361-202 open-label extension study med start date and the record does not exist in 361-201 database [‡] , then 361-202 AE
Partial, known components show that it is on or after 361-202 open-label extension study med start date	Missing	If start date & time >= 361-202 open-label extension study med start date & time, then 361-202 AE If start date > 361-202 open-label extension study med start date, then 361-202 AE If start date = 361-202 open-label extension study med start date and the record exists in 361-201 database [‡] , then 361-201 pre-treatment event or 361-201 AE* If start date = 361-202 open-label extension study med start date and the record does not exist in 361-201 database [‡] , then 361-202 AE

Document: Documentation\SAP

Author:

Version Number:
 Version Date:

Final V1.0
 27FEB2019

Template No: CS_TP_BS016 Revision 4
 Effective Date: 01Apr2016

Reference: CS_WI_BS005

Statistical Analysis Plan

START DATE	STOP DATE	ACTION
Missing	Known	
If stop date & time < 361-202 open-label extension study med start date & time, then 361-201 pre-treatment event or 361-201 AE*
 
If stop date < 361-202 open-label extension study med start date, then 361-201 pre-treatment event or 361-201 AE*
 
If stop date & time >= 361-202 open-label extension study med start date & time and the record exists in 361-201 database[‡], then 361-201 pre-treatment event or 361-201 AE*
 
If stop date & time >= 361-202 open-label extension study med start date & time and the record does not exist in 361-201 database[‡], then 361-202 AE
 
If stop date >= 361-202 open-label extension study med start date and the record exists in 361-201 database[‡], then 361-201 pre-treatment event or 361-201 AE*
 
If stop date >= 361-202 open-label extension study med start date and the record does not exist in 361-201 database[‡], then 361-202 AE

Document: Documentation\SAP

Author:

Version Number:

Final V1.0

Version Date:

27FEB2019

Template No: CS_TP_BS016 Revision 4
 Effective Date: 01Apr2016

Reference: CS_WI_BS005

START DATE	STOP DATE	ACTION
Missing	Partial	
Impute stop date as latest possible date (i.e. last day of month if day unknown or 31st December if day and month are unknown).
 
Then:
 
If stop date & time < 361-202 open-label extension study med start date & time, then 361-201 pre-treatment event or 361-201 AE*
 
If stop date < 361-202 open-label extension study med start date, then 361-201 pre-treatment event or 361-201 AE*
 
If stop date & time >= 361-202 open-label extension study med start date & time and the record exists in 361-201 database[‡], then 361-201 pre-treatment event or 361-201 AE*
 
If stop date & time >= 361-202 open-label extension study med start date & time and the record does not exist in 361-201 database[‡], then 361-202 AE
 
If stop date >= 361-202 open-label extension study med start date and the record exists in 361-201 database[‡], then 361-201 pre-treatment event or 361-201 AE*
 
If stop date >= 361-202 open-label extension study med start date and the record does not exist in 361-201 database[‡], then 361-202 AE

Missing	Missing	
If the record exists in 361-201 database[‡], then 361-201 pre-treatment event or 361-201 AE*
 
If the record does not exist in 361-201 database[‡], then 361-202 AE

Document: Documentation\SAP

Author:

Version Number:
Version Date:

Final V1.0
27FEB2019

Template No: CS_TP_BS016 Revision 4
Effective Date: 01Apr2016

Reference: CS_WI_BS005

ALGORITHM FOR PRIOR / CONCOMITANT / POST-TREATMENT MEDICATIONS:

The concept of “date” below should also include time information whenever available.

For the case where the medication start date is known and is equal to the end of treatment date, and the medication start time is unknown, or the case where the imputed medication start date is equal to the end of treatment date:

- If CRF question ‘*Started after last dose of study medication?*’ = No, then assign as concomitant.
- If CRF question ‘*Started after last dose of study medication?*’ = Yes, then assign as post treatment.

START DATE	STOP DATE	ACTION
Known	Known	If stop date < open-label extension study med start date, assign as prior. If stop date >= open-label extension study med start date and start date <= end of open-label treatment, assign as concomitant. If stop date >= open-label extension study med start date and start date > end of open-label treatment, assign as post treatment.
Known	Partial	Impute stop date as latest possible date: 
 • If only day unknown, impute as the earlier of (last day of the month; end date of the last open-label study visit). • If month and day unknown, impute as the earlier of (31st December; end date of the last open-label study visit). Then: If stop date < open-label extension study med start date, assign as prior. If stop date >= open-label extension study med start date and start date <= end of open-label treatment, assign as concomitant. If stop date >= open-label extension study med start date and start date > end of open-label treatment, assign as post treatment.
Known	Missing	If stop date is missing could never be assumed a prior medication. If start date <= end of open-label treatment, assign as concomitant. If start date > end of open-label treatment, assign as post treatment.

Document: Documentation\SAP

Author:

Version Number:
 Version Date:

Final V1.0
 27FEB2019

Template No: CS_TP_BS016 Revision 4
 Effective Date: 01Apr2016

Reference: CS_WI_BS005

START DATE	STOP DATE	ACTION
Partial	Known	
Impute start date as earliest possible date: CRF questions: 'Started prior to study?' = Yes; 'Started after last dose of study medication?' = No.
 
 • If only day unknown, impute as the later of (first day of the month; date of birth). • If month and day unknown, impute as the later of (1st January; date of birth). 
CRF questions: 'Started prior to study?' = No; 'Started after last dose of study medication?' = Yes.
 
 • If only day unknown, impute as the later of (first day of the month; end of open-label treatment + 1). • If month and day unknown, impute as the later of (1st January; end of open-label treatment + 1). 
CRF questions: 'Started prior to study?' = No; 'Started after last dose of study medication?' = No.
 
 • If only day unknown, impute as the later of (first day of the month; start date of the first open-label study visit [Visit 1E]). • If month and day unknown, impute as the later of (1st January; start date of the first open-label study visit [Visit 1E]). 
Then: If stop date < open-label extension study med start date, assign as prior. If stop date >= open-label extension study med start date and start date <= end of open-label treatment, assign as concomitant. If stop date >= open-label extension study med start date and start date > end of open-label treatment, assign as post treatment.

Document: Documentation\SAP

Author:

Version Number:
Version Date:

Final V1.0
27FEB2019

Template No: CS_TP_BS016 Revision 4
Effective Date: 01Apr2016

Reference: CS_WI_BS005

Statistical Analysis Plan

START DATE	STOP DATE	ACTION
Partial	Partial	
Impute start date as earliest possible date: CRF questions: 'Started prior to study?' = Yes; 'Started after last dose of study medication?' = No.
 
 • If only day unknown, impute as the later of (first day of the month; date of birth). • If month and day unknown, impute as the later of (1st January; date of birth). 
CRF questions: 'Started prior to study?' = No; 'Started after last dose of study medication?' = Yes.
 
 • If only day unknown, impute as the later of (first day of the month; end of open-label treatment + 1). • If month and day unknown, impute as the later of (1st January; end of open-label treatment + 1). 
CRF questions: 'Started prior to study?' = No; 'Started after last dose of study medication?' = No.
 
 • If only day unknown, impute as the later of (first day of the month; start date of the first open-label study visit [Visit 1E]). • If month and day unknown, impute as the later of (1st January; start date of the first open-label study visit [Visit 1E]). 
Impute stop date as latest possible date:
 
 • If only day unknown, impute as the earlier of (last day of the month; end date of the last open-label study visit). • If month and day unknown, impute as the earlier of (31st December; end date of the last open-label study visit). 
Then: If stop date < open-label extension study med start date, assign as prior. If stop date >= open-label extension study med start date and start date <= end of open-label treatment, assign as concomitant. If stop date >= open-label extension study med start date and start date > end of open-label treatment, assign as post treatment.

Document: Documentation\SAP

Author:

Version Number:
 Version Date:

Final V1.0
 27FEB2019

Template No: CS_TP_BS016 Revision 4
 Effective Date: 01Apr2016

Reference: CS_WI_BS005

START DATE	STOP DATE	ACTION
Partial	Missing	
Impute start date as earliest possible date: CRF questions: 'Started prior to study?' = Yes; 'Started after last dose of study medication?' = No.
 
 • If only day unknown, impute as the later of (first day of the month; date of birth). • If month and day unknown, impute as the later of (1st January; date of birth). 
CRF questions: 'Started prior to study?' = No; 'Started after last dose of study medication?' = Yes.
 
 • If only day unknown, impute as the later of (first day of the month; end of open-label treatment + 1). • If month and day unknown, impute as the later of (1st January; end of open-label treatment + 1). 
CRF questions: 'Started prior to study?' = No; 'Started after last dose of study medication?' = No.
 
 • If only day unknown, impute as the later of (first day of the month; start date of the first open-label study visit [Visit 1E]). • If month and day unknown, impute as the later of (1st January; start date of the first open-label study visit [Visit 1E]). 
Then: If stop date is missing could never be assumed a prior medication. If start date <= end of open-label treatment, assign as concomitant. If start date > end of open-label treatment, assign as post treatment.

Missing	Known	
If stop date < open-label extension study med start date, assign as prior. If stop date >= open-label extension study med start date and CRF question 'Started after last dose of study medication?' = No, assign as concomitant. If CRF question 'Started after last dose of study medication?' = Yes, assign as post treatment.

Document: Documentation\SAP

Author:

Version Number:
 Version Date:

Final V1.0
 27FEB2019

Template No: CS_TP_BS016 Revision 4
 Effective Date: 01Apr2016

Reference: CS_WI_BS005

START DATE	STOP DATE	ACTION
Missing	Partial	
Impute stop date as latest possible date:
 
 • If only day unknown, impute as the earlier of (last day of the month; end date of the last open-label study visit). • If month and day unknown, impute as the earlier of (31st December; end date of the last open-label study visit). 
Then:
 
If stop date < open-label extension study med start date, assign as prior.
 
If stop date >= open-label extension study med start date and CRF question 'Started after last dose of study medication?' = No, assign as concomitant.
 
If CRF question 'Started after last dose of study medication?' = Yes, assign as post treatment.

Missing	Missing	
If CRF question 'Started after last dose of study medication?' = No, assign as concomitant.
 
If CRF question 'Started after last dose of study medication?' = Yes, assign as post treatment.

Document: Documentation\SAP

Author:

Version Number:
 Version Date:

Final V1.0
 27FEB2019

Template No: CS_TP_BS016 Revision 4
 Effective Date: 01Apr2016

Reference: CS_WI_BS005

PARTIAL DATE IMPUTATION RULES FOR INITIAL ONSET OF SCHIZOPHRENIA:

For subjects with partial onset dates of schizophrenia, impute the onset date using the following rules:

- If only day unknown, impute as the earlier of: 15th of the month, or date of 361-201 ICF.
- If both month and day unknown, impute as the earlier of: June 30th of the year, or date of 361-201 ICF.

PARTIAL DATE IMPUTATION RULES FOR ONSET OF ACUTE EXACERBATION:

For subjects with partial onset dates of acute exacerbation, impute the onset date using the following rules:

- If only day unknown, impute as the later of: 15th of the month, or date of initial onset of schizophrenia (actual or imputed).
- If both month and day unknown, impute as the later of: June 30th of the year, or date of initial onset of schizophrenia (actual or imputed).

Document: Documentation\SAP

Author:

Version Number:
Version Date:

Final V1.0
27FEB2019

Template No: CS_TP_BS016 Revision 4
Effective Date: 01Apr2016

Reference: CS_WI_BS005

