3.6. CHANGES IN THE CONDUCT OF THE STUDY

The first subject entered study SEP361-202 under protocol version 2.00 (23 June 2016). The protocol versions and amendments listed below were implemented after the enrollment of the first subject:

- Protocol version 3.00 (22-Mar-2017); Amendment 2.00 (22-Mar-2017)
- Protocol version 3.01 (17-Aug-2017); Non-substantial Amendment 1.00 (17-Aug-2017)
- Protocol version 4.00 (13-Oct-2017); Amendment 3.00 (13-Oct-2017)

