11. DEMOGRAPHIC AND OTHER BASELINE CHARACTERISTICS

Demographic data and other baseline characteristics will be presented for the safety population. No statistical testing will be carried out for demographic or other baseline characteristics. The following demographic and other baseline characteristics will be reported for this study:

Document: Documentation\SAP

Author:

Version Number:
 Version Date:

Final V1.0
 27FEB2019

Template No: CS_TP_BS016 Revision 4
 Effective Date: 01Apr2016

Reference: CS_WI_BS005

Statistical Analysis Plan

- Age (years), calculated relative to date of informed consent of study 361-201; as a continuous variable and categorically
 - o <18
 - o 18 to <25
 - o 25 to <=40
 - o >40
- Sex
- Race
 - o American Indian or Alaska Native
 - o Asian
 - o Black or African American
 - o Native Hawaiian or Other Pacific Islander
 - o White
 - o Multiracial
 - o Other
- Ethnicity
 - o Hispanic or Latino
 - o Not Hispanic or Latino
- Country
- Geographic region
- DB Baseline and OL Baseline for Weight (kg)
- Height (cm)
- DB Baseline and OL Baseline for Waist circumference (cm)
- DB Baseline and OL Baseline for BMI (kg/m²), as a continuous variable and categorically:
 - o Underweight: <18.5
 - o Normal: 18.5 to <25.0
 - o Overweight: 25.0 to <30.0
 - o Obese: >=30.0
- DB Baseline and OL Baseline for PANSS total score and subscale scores, as continuous variables and categorically:
 - o < Overall median value at baseline
 - o >= Overall median value at baseline
 - o Positive subscale score < Negative Subscale score
 - o Positive subscale score >= Negative Subscale score

Document: Documentation\SAP

Author:

Version Number:
 Version Date:

Final V1.0
 27FEB2019

Template No: CS_TP_BS016 Revision 4
 Effective Date: 01Apr2016

Reference: CS_WI_BS005

Statistical Analysis Plan

- DB Baseline and OL Baseline for CGI-S score, as a continuous variable and categorically:
 - o < 4
 - o >= 4 to <=5
 - o > 5

The following psychiatric history data will be summarized for the safety population in a separate table:

- Time since initial onset of schizophrenia, in years, calculated relative to date of informed consent of study 361-201; both as a continuous variable and categorically
 - o < 5
 - o >= 5 to < 10
 - o >= 10 to < 20
 - o >= 20
- Time since onset of current acute exacerbation of psychotic symptoms, in days, calculated relative to date of informed consent of study 361-201

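### Partial onset dates of the acute exacerbation are imputed without a cap at consent, so the reported time since onset could be negative

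*SAP*

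**What the plan says.** SAP Section 11 lists, among the psychiatric history variables, "Time since onset of current acute exacerbation of psychotic symptoms, in days, calculated relative to date of informed consent of study 361-201". It is summarised in days and, unlike time since initial onset, has no categories.

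SAP Appendix 2 gives two adjacent sets of rules for partial dates.

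- **Initial onset of schizophrenia.** Day unknown: "If only day unknown, impute as the earlier of: 15th of the month, or date of 361-201 ICF". Month and day unknown: "If both month and day unknown, impute as the earlier of: June 30th of the year, or date of 361-201 ICF". Both take the earlier date, so the result cannot fall after consent to 361-201.
- **Onset of the acute exacerbation.** Day unknown: "If only day unknown, impute as the later of: 15th of the month, or date of initial onset of schizophrenia (actual or imputed". Month and day unknown: "If both month and day unknown, impute as the later of: June 30th of the year, or date of initial onset of schizophrenia". Both take the later date, so there is a floor at initial onset and no ceiling.

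No other part of the SAP caps the imputed exacerbation date or truncates a negative duration. Appendix 2 also says that imputed dates are not shown in the listings.

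**The concern.** An exacerbation described as current at consent began on or before the consent date. If its onset is recorded only as a month, that month is the consent month, and the subject consented on the 10th, the rule dates onset to the 15th and the duration becomes -5 days. The same happens with a year-only date when consent falls before June 30 of that year.

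The floor at initial onset does not help. Initial onset is itself on or before consent (and capped there when partial), so taking the later of two dates never moves the imputed date back towards consent.

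What is at stake is the description of how acute the illness was at entry. A negative minimum would be an evident error in a baseline table, and any affected values would pull the mean down. Because imputed dates are not listed, a reader could not trace such a value to the imputation.

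**Working it through.** The plan states no figure to reproduce, so the check applies the written rules to the calendar.

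**Inputs.** The imputation rules come from SAP Appendix 2 and the reference date (361-201 consent) from SAP Section 11. Assumptions: true onset is on or before consent; duration = consent date - imputed onset date, with no added day; the calendar year is 2017, a 365-day year.

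**Extremes.**
- Day unknown: consent on the 1st, onset imputed to the 15th: 1 - 15 = -14 days.
- Month and day unknown: consent on 1 January (day 1), onset imputed to June 30 (day 181): 1 - 181 = -180 days.
- A leap year would give -181, but SAP Section 3.6 says "The first subject entered study SEP361-202 under protocol version 2.00 (23 June 2016". Consent for that first extension subject came about 28 days plus screening before entry. For an assumed 0 to 28 days of screening and entry on 23 June 2016, consent falls between 28 April and 26 May 2016, giving -63 to -35 days. So -180 stands as the limit.
- An onset recorded in an earlier month or year is not a problem: onset February 2017 with consent on 1 March 2017 gives +14 days.

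**How often, given a partial date in the consent month or year.** The documents give no distribution of the time from onset to consent. I took each consent date as equally likely and the true lag as uniform on 0 to L days, with L from 14 to 365, and counted the (consent, onset) pairs that share the month or year.

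*Day unknown, same month.* Consent on day k leaves min(k, L+1) possible onset days in that month. The value is negative for k = 1 to 14.
- Negative pairs: 12 × (1 + ... + 14) = 12 × 105 = 1,260 for every L of 14 or more.
- All pairs, L = 14: a month of n days has 105 + 15 × (n - 14) pairs. Over the year, 7 × 360 + 4 × 345 + 315 = 4,215. Share: 1,260/4,215 = 30%.
- All pairs, L long enough to cover the month: n(n + 1)/2 per month. Over the year, 7 × 496 + 4 × 465 + 406 = 5,738. Share: 1,260/5,738 = 22%.
- Mean negative value: -Σk(15 - k)/105 = -560/105 = -5.3 days in all cases.

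*Month and day unknown, same year.* Consent on day j of the year leaves min(j, L+1) possible onset days. The value is negative for j = 1 to 180.

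| L (days) | Negative pairs / all pairs | Share negative | Mean negative value (days) |
|---|---|---|---|
| 14 | 2,595 / 5,370 | 48% | -87 |
| 60 | 9,150 / 20,435 | 45% | -77 |
| 180 | 16,290 / 49,775 | 33% | -61 |
| 365 | 16,290 / 66,795 | 24% | -61 |

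**Effect on the mean.** With about 180 subjects (SAP Section 3.3), one year-only negative case moves the mean, relative to a value of 0, by 61/180 = 0.3 to 87/180 = 0.5 day. At the extreme it is 180/180 = 1 day.

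**After a cap at consent.** The minimum is 0 days under both rules for every consent date in 2016, 2017 and 2018.

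**The case against.** The strongest reply is that this may never happen. It needs a partial exacerbation date, in the consent month or year, in a subject who consented before the 15th or June 30, and nothing in the documents shows that even one such date exists. The variable appears once, in a descriptive table. It is not a subgroup factor: SAP Section 7.4 uses duration of schizophrenia, which rests on initial onset and so on the capped rule. No efficacy, relapse or safety analysis uses it. The median and quartiles, which the output conventions in SAP Appendix 1 cover, would hardly move, and a negative minimum would probably be noticed. SAP Section 20 allows for changes during analysis to be described and justified in the final report. All of this stands, and it limits the importance of the point. It does not make the rule correct as written.

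Two stronger readings are tempting and should be resisted.

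- A reader might count consent dates and infer that nearly half of the cases go wrong: 12 × 14 = 168 of 365 dates (46%) fall before the 15th, and 180 of 365 (49%) before June 30. That treats an onset in the consent month as equally likely whatever the day of consent. Onset must precede consent, so a subject who consents on the 3rd has three possible onset days in that month and one who consents on the 28th has up to 28. Allowing for this lowers the day-unknown share to 22-30%. For year-only dates, 49% lies just above the 24-48% range.
- A reader might take -14 and -180 days as the scale of the error. Each requires onset on the day of consent itself, on the 1st of the month or on 1 January, yet with the day, or the month and day, not recorded. They are limits, not typical values.

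**Conclusion.** The point holds as a gap in a derivation rule: as written, the exacerbation rules can return an impossible negative duration, and nothing elsewhere in the SAP prevents it. No figure stated in the plan is wrong.

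Given a partial date in the consent month, about 22-30% of cases would be negative, by about 5 days on average. Given a year-only date in the consent year, about 24-48% would be negative, by about 61 to 87 days on average. These ranges rest on uniform consent dates, a uniform lag with an upper limit of 14 to 365 days, and no added day in the duration; counting an added day would make the extremes -13 and -179. How many subjects are affected is unknown and may be none, so the documents support saying that the table could show negative values, not that it will.

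The consequence is confined to one descriptive psychiatric history variable. This is a minor correction, worth making because it is so cheap.

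**What to change.** In both exacerbation rules of SAP Appendix 2, keep the later of (15th of the month, or June 30) and initial onset, and add that the result may not be later than the date of 361-201 consent. As a formula: imputed onset = min(max(15th or June 30, initial onset), 361-201 consent date). This is the ceiling that the initial-onset rules already use.

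The cost is one phrase in each rule and one line of code. There is a small downside: every affected subject is set to exactly 0 days, so impossible values disappear but the true duration is still understated. Under the same uniform-lag assumption, the mean true duration in the affected day-unknown cases is Σk(k - 1)/2 ÷ 105 = 455/105 = 4.3 days (k = 1 to 14), so the remaining bias there is small. It is larger for year-only dates. A footnote giving the number of subjects with an imputed exacerbation onset would let a reader judge whether it matters.
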